### 13. Participant timeline:

Activity	Staff member	-1 1 month before intervention	T Intervention (Zero point)	F2 Follow up (6 months)	F3 Follow up (12 months)
Recruitment	[name] [name]	X			
Diagnosis	[name]	X			
Consent	[name]	X			
Baseline data collection	[name]	X			
Cavity preparation	[name]		X		
Randomization	[name]		X		
Application of interventions	[name]		X		
Outcome assessment	[name]			X	X

### 14. Sample size calculation:

The sample size was calculated based on a previous study by *Vural et al in 2021*, in which percentage of successful class V restorations (Score A and B) using resin modified glass ionomer regarding marginal discoloration was 68.7%. By implementing a two tailed Z test for difference between two independent proportions with an alpha level of 5% and a power of 80%. The minimum sample size needed was 23 per group in order to detect a difference of 30%. Sample size was increased by 20% to compensate for possible dropouts to reach 28 teeth per group. Sample size was performed using G\*Power version 3.1.9.2 for windows.

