## **B) Study Objectives:**

### **7. Aim of the study:**

This study is conducted to evaluate the clinical performance of low-shrinkage giomer resin composite versus resin-modified glass ionomer in restoration of cervical caries lesions, using both Modified USPHS and Revised FDI criteria.

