### **Hypothesis:**

This study will be designed to test the null hypothesis that the low-shrinkage giomer resin composite will have the same clinical performance as resin-modified glass ionomer in cervical restorations, using both Modified USPHS and Revised FDI criteria.

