### **Primary Objectives:**

Measure the functional, biological, and aesthetic properties of both restorations (using Revised FDI criteria for direct restorations) at baseline, after 6, and 12 months.

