#### **b) Secondary Objectives:**

Measure Cost-Effectiveness Analysis: Cost-effectiveness will be assessed by calculating the Incremental Cost-Effectiveness Ratio (ICER) and the Cost per Success Ratio (CPSR).

**T (Time):** 12 months; with follow up at baseline, 6, and 12 months.

**S (Study design):** Randomized clinical trial.

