## 12. Outcomes

Outcomes will be assessed by mouth mirror, dental explorer, standardized photographs and FDI probe according to modified USPHS criteria and Revised FDI criteria for direct and indirect restorations:

- **Primary outcomes:** All restorations will be assessed for functional, biological, and aesthetic properties using Revised FDI criteria for direct and indirect restorations. They will be given a score (clinically excellent/very good, clinically good, clinically satisfactory, clinically unsatisfactory, clinically poor).
- **Secondary outcomes:** Cost-Effectiveness Analysis

Cost-effectiveness will be assessed by calculating the Incremental Cost-Effectiveness Ratio (ICER) and the Cost per Success Ratio (CPSR). These metrics will be used to compare the cost and clinical outcomes of LS-GRC and RMGI in treating class V cavities.

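### The stated 80% power belongs to one marginal-discoloration item that no outcome list names; it is not supported for the listed ordinal FDI primary outcome, which has no primary property, cut-off or between-group multiplicity rule

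*Combined protocol and SAP*

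**What the plan says.** **Sample size (section 14).** The control rate comes from a previous study "in which percentage of successful class V restorations (Score A and B) using resin modified glass ionomer regarding marginal discoloration was 68.7"%. A two-sided Z test for two independent proportions at 5% alpha and 80% power, with a difference of 30%, gives 23 per group. This is raised by 20% to 28.

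**Objectives and outcomes.** The primary objective is to measure functional, biological and aesthetic properties, "using Revised FDI criteria for direct restorations) at baseline, after 6, and 12 months". Section 12 says "All restorations will be assessed for functional, biological, and aesthetic properties using Revised FDI criteria for direct and indirect restorations" and then "They will be given a score" on five categories from excellent to poor. The table in section 20b lists the same primary outcome as ordinal scores on the Revised FDI criteria. None of these places names marginal discoloration.

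**Second scale.** The aim refers to performance "in restoration of cervical caries lesions, using both Modified USPHS and Revised FDI criteria". The null hypothesis is that the giomer "will have the same clinical performance as resin-modified glass ionomer in cervical restorations, using both Modified USPHS and Revised FDI criteria". Section 12 says assessment is "according to modified USPHS criteria and Revised FDI criteria for direct and indirect restorations". The table in section 20b has no modified USPHS entry.

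**Analysis (section 20a).** Groups are compared by chi-square. Within-group changes are tested by Cochran's Q with pairwise follow-up. Every test uses p ≤ 0.05, and 80% is given as the power of the study.

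**Timing.** The PICOTS time entry reads "12 months; with follow up at baseline, 6, and 12 months". This makes 12 months the natural primary visit, but no section designates it as such.

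**The concern.** The quantity that was powered and the quantity that is listed as primary are not shown to be the same. The first is a two-category success rate on one item. The second is a five-level score covering three groups of properties. A power figure belongs to a particular endpoint, test and alternative, and it cannot be carried over to another endpoint without that endpoint's own rates or distribution.

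The rule for the primary conclusion is also open. Section 12 does not say whether a restoration gets one score or one per property group, so the number of primary tests is unknown. No cut-off turns the score into success or failure, although Cochran's Q needs a binary variable. The only success definitions sit with the cost outcomes: section 12 uses a clinically excellent rate for the ICER, and both a no-failure and a clinically excellent wording for the CPSR. The only multiple-comparison wording in section 20a applies within a group.

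At stake are two things: a final report could attach 80% power to an outcome for which it was never derived, and the property, cut-off or visit that decides the null could be chosen after the data are seen.

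**Working it through.** **1. Reproduce the plan's figure.** Inputs from section 14: p₁ = 0.687, difference 0.30, two-sided α = 0.05 (z = 1.960), power 80% (z = 0.842). The upward alternative is p₂ = 0.987, with mean p̄ = 0.837.

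n = [1.960·√(2p̄(1−p̄)) + 0.842·√(p₁(1−p₁) + p₂(1−p₂))]² / 0.30²

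The two roots are 0.5224 and 0.4773, so n = (1.0238 + 0.4018)² / 0.09 = 22.58, hence **23**. Then 23 × 1.2 = 27.6, hence **28**. Both figures match the plan. The opposite direction, 0.687 against 0.387, gives 42.2, hence 43. The plan's 23 therefore implies a giomer rate of 98.7%.

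**2. Power for the sized item.** The normal formula is Φ[(0.30·√n − 1.0238)/0.4773]. The exact figure sums both binomials over all tables where the uncorrected chi-square is significant.

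| n per group | Normal | Exact |
|---|---|---|
| 23 | 80.8% | 89.8% |
| 28 | 88.1% | 95.2% |

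There is no shortfall for marginal discoloration at 68.7% against 98.7%.

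**3. Power for the listed primary outcome.** This would need at least a named property, a cut-off with a control rate and a target difference, or else a distribution over the five categories in each arm. The documents give none of these for any FDI property. The power cannot be computed, so it can be called neither adequate nor inadequate.

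**4. Error rate if there are three primary tests.** Assumptions: each property group has its own score, one test per group is done at 12 months, and any one significant result rejects the null of equal performance.

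- Independent tests at full 5% size: 1 − 0.95³ = 14.3%.
- Correlation 0.8 between the three test statistics (assumed; simulation with 1,000,000 draws of three equicorrelated normals): 9.8%.
- If scores are cut to success or failure and both groups have 95% success (assumed), the exact chi-square size is only 1.64% at n = 23 and 2.50% at n = 28. Three independent tests then give 1 − (1 − 0.0164)³ = 4.8% and 1 − (1 − 0.0250)³ = 7.3%.
- At 70%, 80% and 90% success the exact size is 4.5% to 5.3% per test, so the nominal 5% is a fair approximation there.
- If one overall score per restoration is meant, there is one between-group test at 12 months and no inflation across properties.

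**5. What adjustment would do (illustration only).** With the discoloration rates borrowed and α = 0.05/3 (z = 2.394), the normal formula gives Φ[(0.30·√n − 2.394 × 0.5224)/0.4773].

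| n per group | Normal | Exact |
|---|---|---|
| 23 | 65.3% | 67.9% |
| 28 | 76.0% | 82.7% |

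These are lower bounds per test under Holm. They are not estimates of power for any FDI property.

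**The case against.** **Discoloration may already be inside the primary outcome.** The plan adopts the Revised FDI criteria by reference and does not list their items, so discoloration could be one of the aesthetic items. This stands to the extent that a reader might infer that the item lies outside the primary outcome, or could only be recorded under modified USPHS, and the documents do not support either inference. They simply do not name it. Even if it were an FDI item, it would be one item within one of three property groups, and the letter scoring used for sizing is not the five-category scoring of section 12.

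**The sample size is correct.** It is, for the item it describes. A reader might infer that the trial is underpowered. The documents do not show that: power for the sized item meets the target, and power for the FDI outcome is unknown rather than shown to be low.

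**The 80% in section 20a may only repeat section 14.** That is a possible reading. But it is worded as the power of the study, and it stands in the analysis plan next to a different primary outcome without qualification.

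**The false-positive figure is conditional.** This is correct. It needs a score per property group and a rule that any one property may reject, and the plan states neither. The 0.8 correlation is an assumption too; higher correlation would give less inflation. Nor does the plan say that chi-square would be run on a two-category version of the score, which the exact sizes assume. A flat claim that the trial has a 14% type I error would not be supported.

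**Conclusion.** The point holds as a mismatch between the powered item and the listed primary outcome, together with an undefined primary endpoint. The figures of 23 and 28 per group are arithmetically sound, and the stated 80% is met for 68.7% against 98.7% on marginal discoloration at α = 0.05. It is not supported for the ordinal FDI outcome, whose power cannot be derived from the documents.

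The possible error inflation, about 10% to 14% against a nominal 5%, rests on three separate scores, an any-property rule, and tests with close to full 5% size. It is smaller when success is near 95% or more, and absent across properties if one score per restoration is intended. The mismatch in the power statement and the missing cut-off remain under either reading. They should be corrected before outcome data are analysed, because the choice of endpoint decides what the trial can confirm.

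**What to change.** **Preferred: one primary endpoint.** In sections 12, 14 and 20, name one endpoint at 12 months and give its cut-off. It can be either:

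- the marginal-discoloration item used for sizing, listed as an outcome in sections 12 and 20b, with USPHS and FDI scoring reconciled; or
- one FDI endpoint, with its own assumed control rate and a restated power.

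State whether each restoration gets one score or one per property group, and make all other properties and visits secondary.

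**Alternative: three co-primary FDI property groups at 12 months.** Give a cut-off and an assumed control rate for each, apply Holm across the three, and restate the power from those rates. The downside is that it may fall below 80%, as the illustration above shows: 65% (normal) or 68% (exact) at 23 per group, and 76% or 83% at 28.

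**In either case.** State in sections 14 and 20a that the present 80% applies only to 68.7% against 98.7% on marginal discoloration at α = 0.05. Either add modified USPHS to the table in section 20b or remove it from the aim, the hypothesis and section 12.

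**Cost.** Protocol and analysis-plan wording, a possibly lower stated power, and loss of confirmatory status for the other properties and visits. No extra patients are needed if the power is restated and the trial is not re-sized. If the authors want 80% for each of three adjusted tests, more would be needed: with the borrowed discoloration rates at α = 0.05/3, 31 evaluable per group instead of 23.

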### 15. Patient Recruitment:

Patients will be recruited by [name] using stratified sampling method until reaching to the target sample size. They will be recruited from clinic of conservative dentistry department in Faculty of Dentistry, Cairo University, where there is a continuous and high patient flow from which eligible patients will be recruited to fulfill the eligibility criteria 1 month before intervention.

## **B) Assignment of interventions:**

### **16. Allocation:**

#### **16. a) Random sequence generation (Randomization):**

[name] will perform simple randomization according to a check list, including the number of participants by generating numbers from 1 to 56, divided into two groups denoted with letter A and B. Randomization will be generated using ([www.randomization.com](http://www.randomization.com)).

#### **16. b) Allocation concealment mechanism:**

The allocation sequence will be kept with the contributor ([name]) in sealed tight envelopes concealed from the primary investigator. The principal investigator ([name]) will know the allocation of the consented participant just before starting the restorative procedures.

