## **Restorative procedures:**

### **- Cavity preparation procedures for both the intervention and control groups:**

After giving local anesthesia, the operative field will be isolated using rubberdam by performing multiple teeth isolation with at least two teeth before and after tooth to be treated. Using a water-cooled high-speed handpiece (380.000-480.000 rpm), class V cavity will be prepared on the facial surface of the tooth using a pear-shaped diamond bur (MANI Ltd., Utsunomiya, Japan), and then a bevel is prepared 45° on the incisal wall of the cavity using a diamond finishing tapered bur (MANI Ltd., Utsunomiya, Japan). The bur will not be used for more than 3 cavity preparations. Any remaining soft carious dentin will be excavated by a small, sharp excavator (Dentsply® Maillefer, Switzerland).

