### **Intervention:**

Low Shrinkage, giomer paste-like resin composite (Beautifil™ II LS, Shofu Inc, Kyoto, Japan).

All materials will be applied according to the manufacturer's instructions. The prepared tooth surfaces will be rinsed and dried by gently blowing with an air syringe. Selective enamel etching will be done; where the enamel margins will only be etched with 35-40% phosphoric acid gel for 10-15 seconds, rinsed for 5 seconds and gently dried. The unfilled universal adhesive (Shofu Inc, Kyoto, Japan) will be applied onto the entire cavity surface and left undisturbed for 10 seconds. Then the adhesive will be air dried with gentle air for 3 seconds and then, dried with stronger air to dry the surface. It will be light-cured using LED light-curing unit (Light output: 1200 mW/cm^2) for 20 seconds. Beautifil™ II LS will be applied according to manufacturer's instructions as follows: shade selection will be done before rubberdam isolation. The material will be applied into the cavity using a gold-plated instrument, where incremental filling and light-curing of the material in layers, does not exceed 2 mm each. Each increment will be light-cured using LED light-curing unit (Light output: 1200 mW/cm^2) for 20 seconds. The restorations will be finished using water-cooled microfine diamond finishing burs for contouring and removal of excess restorative material and will be polished with aluminum oxide polisher immediately after filling.

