#### **16. c) Implementation**

All participants who fulfill eligibility criteria and who give consent for participation will be randomized by [name] into two groups.

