## **17. Blinding (masking):**

Participants will be blinded to the intervention they were assigned to. Outcome assessors will be blinded as well as statisticians. The principal investigator cannot be blinded due to the difference in manipulation and application of restorative materials

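### The plan does not fix whether the unblinded operator learns the arm before or after the cavity is cut; read literally, section 16b puts it before

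*Combined protocol and SAP*

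**What the plan says.** Five places bear on when the arm becomes known.

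- **Section 16b (allocation concealment).** The sequence is kept by another contributor in sealed envelopes, hidden from the investigator. The principal investigator "will know the allocation of the consented participant just before starting the restorative procedures". Cavity preparation is not mentioned.
- **Section 11, Restorative procedures.** The first block under this heading is "Cavity preparation procedures for both the intervention and control groups". It begins: "After giving local anesthesia, the operative field will be isolated using rubberdam". The cavity is then cut with a specified type of bur, a 45° bevel is placed on the incisal wall, and remaining soft carious dentin is removed by hand. The separate Intervention and Comparator descriptions follow. The Intervention text adds that "shade selection will be done before rubberdam isolation"; the Comparator text does not mention shade.
- **Section 13 (participant timeline).** The rows "Cavity preparation", "Randomization" and application of interventions appear in that order, all marked in the zero-point column.
- **Section 16c (implementation).** "All participants who fulfill eligibility criteria and who give consent for participation will be randomized by" a named contributor into two groups. No timing relative to preparation is given.
- **Section 17 (blinding).** "The principal investigator cannot be blinded due to the difference in manipulation and application of restorative materials". Participants, outcome assessors and statisticians are to be blinded.

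**The concern.** The two materials are meant to be compared in cavities prepared in the same way. An operator who does not know the arm cannot adapt the preparation to the material, whether deliberately or not. An operator who does know it can.

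The reason section 17 gives for not blinding the operator concerns how the materials are handled and placed. It does not extend to a preparation step that is the same in both groups, so nothing in the plan requires the arm to be known at that point.

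The preparation is relevant to what is measured. The statement of the problem attributes most restoration failures to caries where tooth and filling meet and to lost retention, and section 14 bases the sample size on marginal discoloration. The cavity margin is formed during preparation. If preparation differed systematically by arm, part of any observed difference between materials could reflect the cavity and not the material, and blinded assessment afterwards would not remove it.

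**Working it through.** This is a question of sequence, so no arithmetic applies. The check sets the passages side by side.

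**Step 1: what section 16b means in the protocol's own terms.** Disclosure comes just before the restorative procedures. Section 11 uses the same term as a heading, and the first item under it is the preparation common to both groups. Combining the two gives: envelope opened, isolation, preparation, placement. This depends on taking the heading as the definition of the phrase in section 16b. No sentence states outright that disclosure precedes preparation.

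**Step 2: what the timeline implies.** The rows run: recruitment, diagnosis, consent, baseline data, cavity preparation, randomization, application of interventions, outcome assessment. Across columns this is chronological. Randomization also has its own row between preparation and application, which looks deliberate. Section 16a produces the list of 1 to 56 as a single sequence, so a randomization row at the treatment visit most naturally means assignment of the individual participant. If assignment follows preparation, disclosure must follow it too. The limit is that the three rows share one column with no clock order, so the inference rests on row position.

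**Step 3: whether another section settles it.** Section 16c gives no timing relative to preparation. Section 17 says who is unblinded and why, but not from when. Neither decides between steps 1 and 2.

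**Step 4: what could vary if the arm were known.**

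| Element of preparation (section 11) | Fixed by the text? |
|---|---|
| Rubber dam isolation | Yes |
| Type of bur, and limit of 3 preparations per bur | Yes |
| Incisal bevel at 45° | Angle yes, width no |
| Extent of the cavity | No |
| Removal of remaining soft dentin | Instrument yes, end point judged by the operator |

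The method is common to both groups, but cavity extent, bevel width and the end point of excavation remain matters of judgement.

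**Result.** The literal text points to disclosure before preparation, the timeline to disclosure after it, and no section resolves the difference. On the first reading, the judged elements in step 4 are open to influence in all planned restorations (28 + 28 = 56). On the second, the preparation is already protected.

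**The case against.** The strongest reply is that sections 13 and 16b can be reconciled. If restorative procedures in section 16b means placing the restoration, the investigator learns the arm after preparation and before placement, exactly as the timeline lists it. The safeguard would then already be in the plan and section 16b would merely be loosely worded. This is a fair reading, and it is why the point is an unresolved order and not a flat contradiction. It does not remove the need for a change: it requires the phrase to mean something narrower than the protocol's own heading, and an operator following section 16b as written could open the envelope before cutting.

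A second reply is that section 11 prescribes one preparation for both groups. That stands, so no planned difference between arms can be alleged. It does not cover the elements left to judgement.

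A reader might also infer that shade selection gives the arm away, because it is written only for the giomer and precedes the rubber dam. The documents do not support this. Shade can be taken for every participant before disclosure, and the Comparator text defers to the manufacturer's instructions without saying that shade is not taken. Only section 16b, through the heading in section 11, supports disclosure before preparation.

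**Conclusion.** The point holds in a limited form. The documents do not fix one order for disclosure and cavity preparation, and the literal reading of section 16b is the less protective one. On that reading there is an avoidable risk of performance bias in the operator-judged parts of the preparation. On the timeline's reading there is none.

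This assumes that the unblinded principal investigator also cuts the cavities. Section 17 implies that this person places the restorations, but staff names in the timeline are not available to confirm who prepares.

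Two stronger conclusions that a reader might draw are not supported:

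- **Selection bias or failed concealment.** Diagnosis and consent are scheduled a month before treatment, and another person holds the sealed envelopes. The eligibility criteria contain none that is applied to the prepared cavity. Section 20c keeps all randomized participants in their assigned groups, so dropping one after disclosure would depart from the plan.
- **A stated size of bias.** Nothing in the documents indicates how far knowledge of the arm would shift the preparation or the outcome. Any number of percentage points would be invented, so none is given.

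The case for acting rests on the change costing almost nothing, not on a demonstrated effect. It is a free improvement.

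**What to change.** - **Section 16b:** state that the envelope is opened only after the cavity preparation common to both groups is complete. This is the order the timeline already suggests.
- **Section 11:** mark the point of disclosure between the common preparation and the separate Intervention and Comparator steps, so that the heading no longer pulls section 16b the other way.
- **Section 13:** keep the row order and add a note that the steps within the zero-point column are sequential.
- **Shade:** if shade is recorded before isolation, do so for all participants, before disclosure.

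No new eligibility check on the prepared tooth is needed. The cost is a few sentences of wording and opening the envelope later in the same visit, with no additional staff, visits or participants and no effect on sample size or analysis.
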